1.1.3 Nonclinical

1.1.3.1 Safety

In a nonclinical setting, single-dose toxicology studies of cannabidiol reveal a relatively safe toxicology profile except at very high doses of the drug substance. Repeated dose toxicology studies highlight a potential impact of cannabidiol on spermatogenesis, follicle-stimulating hormone (FSH) levels, and a subset of immune responses. Full detail of these results may be found in the IB¹ and selected data are summarized below.

- In a repeated-dose toxicity study, monkeys treated with oral cannabidiol (0, 30, 100, or 300 mg/kg/day), spermatogenesis was inhibited.³⁶ Another study reported abnormal sperm in animals exposed to cannabidiol and that paternal exposure to cannabidiol is associated with a lower impregnation rate, a 2.3-fold increase in fetal loss, and a 5.2-fold increase in postnatal loss.³⁷
- Levels of FSH increased approximately 70% to 100% in Rhesus monkeys dosed with 100 and 300 mg/kg/day of cannabidiol.³⁸
- Blood sampling following repeated daily injections of 5 mg/kg/day cannabidiol for 14 days in adult male Wistar rats showed decreased total leukocyte number and total numbers of T and B cells and T helper and T cytotoxic subsets.³⁹ This immunosuppressive effect did not affect the total numbers of natural killer (NK) and NK T cells that are responsible for the primary, nonspecific antiviral, and antitumor immune response. Mechanistically, 0.5 to 10 μ M of cannabidiol suppressed interleukin-2 (IL-2) and interferon (IFN)- γ messenger ribonucleic acid (mRNA) expression, proliferation, and cell surface expression of the IL-2 receptor α chain in murine splenocyte cell suspensions.
- Human peripheral lymphocytes cultured with 3.2×10^{-6} M cannabidiol for 72 hours did not induce chromosomal aberrations.⁴⁰ Similarly, treatment with 20 to 250 μ M cannabidiol did not induce unscheduled deoxyribonucleic acid (DNA) repair synthesis in cultured human fibroblasts.⁴¹ Cultured lymphocytes harvested from prior *cannabis* users receiving oral doses of 1200 mg/day of cannabidiol for 20 days did not show an increase in chromosomal aberrations or sister chromatid exchange.⁴²
- Intraperitoneal (IP) injection of 1 or 10 mg/kg/day into mice resulted in 2- to 6-fold increases in chromosomal and nuclear aberrations in bone marrow cells harvest from these mice.⁴³
 - Conversely, human peripheral lymphocytes cultured with 3.2×10^{-6} M cannabidiol for 72 hours did not induce chromosomal aberrations.⁴⁴

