1.4 Risk-Benefit Analysis

As discussed in Sections 1.1.3 and 1.1.4, numerous nonclinical and clinical studies have examined other formulations of cannabidiol. Several areas of potential concern have been identified with the use of cannabidiol, especially in nonclinical studies. These include:

- Competitive binding of CYP proteins (thus, an impact on drug metabolism in the liver). Cannabidiol is metabolized predominantly by CYP3A4 and CYP2C19, and may inhibit these 2 isoenzymes, as well as having small effects on CYP3A5, CYP1A1, and CYP2C9
- Abnormal spermatogenesis
- Abnormal induction of FSH in males
- Potential downregulation of immune responses involving the T, B, T-helper, and T cytotoxic subsets of leukocytes and/or those dependent on IL-2 or IFN- γ .

Based on recent studies of cannabinoid administration in humans, controlled cannabidiol may be safe in humans and animals. However, further studies are needed to investigate these reported effects.

The concomitant medication guidelines and safety monitoring (clinical laboratory, ECG, vital signs, and physical and neurological examination assessments) planned for this study (see Sections 4.9 and 6.1) are intended to minimize these potential safety risks. Levels of cannabidiol and its 7-hydroxy (OH) metabolite in the plasma will also be monitored (see Section 6.2).

Stopping criteria for individual subjects will dictate termination of subject participation should a safety issue arise (see Section 3.4.3).

This study will allow subjects who previously completed INS011-14-029 or participated in INS011-15-054 and completed Part A (visit 6) continued access. This is particularly important for those who received therapeutic benefit in terms of seizure control during the previous studies. As reviewed in Section 1.2, patients with treatment-resistant seizure disorders continue to experience a significant unmet medical need despite ongoing treatment with currently available medications and procedures. Devinsky et al.⁷⁷ recently noted that treatment-resistant seizure disorders are particularly good candidates for cannabidiol intervention.

From a therapeutic perspective, the risk of exacerbating a subject's epilepsy symptoms will be minimized by examining the investigational product in an adjunctive setting in combination with the subject's established AED(s) treatment regime. Alternations may be made to the subject's AED background medication(s) as discussed in Section 4.3.

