6.1.4 Clinical Laboratory Evaluations

All clinical laboratory tests will be reviewed for results of potential clinical significance throughout the study. The Investigator will evaluate any change in laboratory values. If the Investigator determines a laboratory abnormality to be clinically significant, it is considered a laboratory AE; however, if the abnormal laboratory value is consistent with a current diagnosis, it may be documented accordingly.

The following laboratory tests will be assessed at the time points specified by Table 1.

- Hematology: complete blood count (CBC) with differential, including platelet count, neutrophils, lymphocytes, eosinophils, basophils, monocytes, hemoglobin, and hematocrit
- Serum chemistry: total protein, albumin, creatinine, blood urea nitrogen (BUN), uric acid, total bilirubin, direct bilirubin, alkaline phosphatase, FSH, AST, ALT, glucose, calcium, phosphorus, bicarbonate, chloride, sodium, and potassium
- Urinalysis: specific gravity, pH, color, and presence of white blood cells (WBCs), red blood cells (RBCs), and proteins
- β -hCG in urine (pregnancy test)

LFTs (e.g., albumin, direct and total bilirubin, AST, and ALT) will be closely monitored to identify any damage that could be induced by the investigational product.

Levels of FSH will be monitored as a potential surrogate outcome for gametocyte damage.

Laboratory values outside the reference limits suspected to be of any clinical significance will be repeated. Subjects in whom suspected clinical significance is confirmed will either not be included or if already enrolled will be followed until normalization or for as long as the Investigator considers necessary. Additional laboratory variables may be performed for safety reasons if judged appropriate by the Investigator. Further details are provided in the Laboratory Manual.

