6.1.5.2 Physical and Neurological Examinations

The full physical examination will consist of the following: general appearance, skin, eyes, ears, nose, throat, neck, lymph nodes, chest, heart, abdomen, and extremities. All physical exams will also include an assessment of the subject's height and weight.

A brief neurological examination will consist of the following: mental status, cranial nerves, nystagmus, motor system, sensory system, reflexes, coordination, gait, and station.

The subject's developmental capabilities will be assessed as a part of the neurological examination (in a manner the Investigator sees fit) during the Screening Period (Visit 1) or Visit 2 (Day 1) only, whichever visit occurs first for each respective subject.

Additional examinations may be performed at the discretion of the Investigator.

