7.4. EXAMINATION OF SUBGROUPS

No subgroup analyses will be performed for this study.

Document: C:\Users\q832483\Documents\Insy CSR\Pending\Ready for QC\New folder\Statistical Analysis Plan.docx
Author: [REDACTED] Version Number: V1.0 Final
Version Date: 04APR2017

Template No: CS_TP_BS016 – Revision 3
Effective Date: 01May2012

Reference: CS_WI_BS005

However analyses will be displayed by age category as follows:

- Infants = 1 to <2 years of age
- Children = 2 to <12 years of age
- Adolescents = 12 to ≤17 years of age

Age categories are based on the subject's age at the beginning of their previous study.

In addition, some relevant results observed during the follow-up period (between the Final visit and the Follow-up visit) or assessed at the Follow-up visit will be presented by CBD status (i.e. subjects who continue to receive CBD after their Final visit versus those who stop receiving CBD after their Final visit). Such analyses are further described in the following sections.

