17.3. LABORATORY EVALUATIONS

Results from the central laboratory will be included in the reporting of this study for Hematology, Serum Chemistry, and Urinalysis. A list of laboratory assessments to be included in the outputs is included in [Appendix 3](#).

Data will be provided and presented in Standard International (SI) units.

Quantitative laboratory measurements reported as “< X”, i.e. below the lower limit of quantification (BLQ), or “> X”, i.e. above the upper limit of quantification (ULQ), will be converted to X for the purpose of quantitative summaries, but will be presented as recorded, i.e. as “< X” or “> X” in the listings.

The following summaries will be provided for laboratory data:

- Actual and change from baseline results will be summarized by time point and age category (for quantitative measurements) using descriptive statistics
- Shift from baseline according to normal range criteria (for quantitative measurements and categorical measurements as described in [Section 17.3.1](#)) by time point and age category
- Proportion of subjects who develop clinical laboratory result abnormalities of interest as described in [Section 17.3.1](#)

Each laboratory result will be compared, separately, to the both baselines as defined [Section 6.2](#).

Each laboratory result measured at the Follow-up visit will also be summarized (as described above) by CBD status.

All laboratory data will be listed with abnormal values flagged.

Data from *Urine Pregnancy Test* and *Blood Draw for Plasma Level* eCRF page will also be listed.

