APPENDIX 3. LABORATORY TESTS

Analytical Testing

Hematology	white blood cells, red blood cells, platelet count, neutrophils, lymphocytes, eosinophils, basophils, monocytes, hemoglobin, and hematocrit
Serum Chemistry	total protein, albumin, creatinine, Blood urine nitrogen (BUN), uric acid, total bilirubin, direct bilirubin, alkaline phosphatase, FSH, AST, ALT, glucose, calcium, phosphorus, bicarbonate, chloride, sodium, and potassium
Urinalysis	specific gravity, pH, color, and presence of white blood cells (WBCs), red blood cells (RBCs), and proteins
Pregnancy test	β human chorionic gonadotropin (β -hCG) in urine

Document: C:\Users\q832483\Documents\Insy CSR\Pending\Ready for QC\New folder\Statistical Analysis Plan.docx
Author: [REDACTED] Version Number: V1.0 Final
Version Date: 04APR2017

Template No: CS_TP_BS016 – Revision 3
Effective Date: 01May2012

Reference: CS_WI_BS005

[figure not shown]

Document: C:\Users\q832483\Documents\Insy CSR\Pending\Ready for QC\New folder\Statistical Analysis Plan.docx
Author: [REDACTED] Version Number: V1.0 Final
Version Date: 04APR2017

Template No: CS_TP_BS016 – Revision 3
Effective Date: 01May2012

Reference: CS_WI_BS005

PHARMACOKINETIC STATISTICAL ANALYSIS PLAN

Insys Development Company
Clinical Trial Protocol INS011-14-030
A multicenter, open-label, flexible dose study to assess the long-term safety of pharmaceutical Cannabidiol Oral Solution as an adjunctive treatment for pediatric and adult subjects with a treatment-resistant seizure disorder who complete INS011-14-029 or Part A of INS011-15-054

Pharmacokinetic Statistical Analysis Plan
11 July 2017

[REDACTED]

Page 2 of 12

Pharmacokinetic Statistical Analysis Plan
Insy Clinical Trial Protocol INS011-14-030

SIGNATURES

Statistician:
Title

[REDACTED]
Ph.D.

Signature/Date:

[REDACTED]
11 July 2017

Pharmacokineticist:
Title

[REDACTED]
Ph.D.

Signature/Date:

[REDACTED]
11 Jul 2017

Pharmacokineticist:
Title

[REDACTED]
Ph.D.

Signature/Date:

[REDACTED]
11 Jul 2017

Sponsor Approval:
Title

[REDACTED]
Ph.D.

Insy Development Company

Signature/Date:

[REDACTED]
11 Jul 2017

[REDACTED]
Page 3 of 12Pharmacokinetic Statistical Analysis Plan
Insys Clinical Trial Protocol INS011-14-030**LIST OF COMMON ABBREVIATIONS AND DEFINITIONS OF TERMS**

ANOVA	analysis of variance
AUC	area under the (plasma concentration vs. time) curve
bid or BID	twice daily
BLQ	below the limit of quantitation
CI	confidence interval
CL/F	clearance after extravascular administration

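### FSH is the only laboratory marker for the named male gonadal concern, but no planned summary shows it by sex, so a within-range group rise in boys would be diluted

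*SAP*

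**What the plan says.** Protocol 1.4 lists "Abnormal spermatogenesis" and "Abnormal induction of FSH in males" among the areas of potential concern. Protocol 1.1.3.1 gives the nonclinical background for the second: "Levels of FSH increased approximately 70% to 100% in Rhesus monkeys dosed with 100 and 300 mg/kg/day of cannabidiol". Protocol 6.1.4 then sets the role of the test: "Levels of FSH will be monitored as a potential surrogate outcome for gametocyte damage".

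The chemistry list in SAP Appendix 3, which matches Protocol 6.1.4, contains FSH and no other reproductive hormone; its last part reads "alkaline phosphatase, FSH, AST, ALT, glucose, calcium, phosphorus, bicarbonate, chloride, sodium, and potassium". The physical examination in Protocol 6.1.5.2 covers "general appearance, skin, eyes, ears, nose, throat, neck, lymph nodes, chest, heart, abdomen, and extremities", with no genital or pubertal item.

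For the analysis, SAP 17.3 states: "Actual and change from baseline results will be summarized by time point and age category (for quantitative measurements) using descriptive statistics". It plans shift tables by the same two factors. SAP 3.3 replaces the protocol's by-dose presentation with age category and overall only. SAP 7.4 says "No subgroup analyses will be performed for this study" and then sets out the three age categories. SAP 10 lists sex only as a demographic item. The protocol's own laboratory section (8.3.4.2) does not split by sex either.

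**The concern.** The concern in Protocol 1.4 is about males, and the study enrols both sexes. A table of FSH that pools boys and girls does not show what happened in boys. If boys rise as a group and girls do not, the pooled mean change understates the rise. If girls' FSH moves for any reason, it can hide a change in boys or look like one. What is at stake is whether the planned summaries can inform the one gonadal concern that the protocol names and chooses a test for.

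The SAP does tailor its output to other risks. Liver tests have markedly abnormal limits (17.3.1). Anemia events get a listing of red-cell values over time, and somnolence is related to clobazam use (17.1.6). Respiratory rate has age-dependent ranges (17.5.1). FSH has nothing comparable beyond the general Low/Normal/High classes and its two event terms in Appendix 2.

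**Working it through.** **The plan's own figure.** There is no figure for FSH and no power calculation. The only relevant number is the maximum sample size in Protocol 8.1: 60 + 20 = 80 subjects, which reproduces.

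**Inputs the documents do not give.** The share of boys (p), the mean FSH by sex and the variability of FSH change by sex. Assumed here: p from 0.4 to 0.6.

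**1. Mean change.** SAP 6.6 defines change as the visit value minus the baseline value, an absolute difference. Let d be the mean change in boys and g the mean change in girls.

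- Pooled mean change = p × d + (1 − p) × g.
- With g = 0 this is p × d: 0.4d, 0.5d and 0.6d for 40%, 50% and 60% boys.
- With g not zero, pooling can hide or imitate a male change. For p = 0.5 and g = −d, the pooled change is 0.5d − 0.5d = 0. For d = 0, it is (1 − p) × g, although boys have not changed.

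A table for boys alone would show d whatever g is.

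**2. Shift counts.** These behave differently. Suppose 80 subjects, 40 of them boys, and 20% of the boys (8) move from Normal to High, with no girls shifting. The boys' table would show 8/40 = 20%; the pooled table shows 8/80 = 10%. For 40% and 60% boys the pooled figures are 0.4 × 20% = 8% and 0.6 × 20% = 12%. The denominator grows, but all 8 boys are still counted. This holds only if the ranges used classify boys correctly; SAP 17.3.1 refers to the relevant laboratory ranges without saying whether they depend on sex.

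**3. A percentage version.** Let r be girls' baseline mean divided by boys' baseline mean, let d now be the boys' relative rise, and assume no change in girls. The pooled relative change is p × d / (p + (1 − p) × r). Putting in the animal rise of 70% to 100%:

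- r = 1, p = 0.5: 35% to 50%.
- r = 1, p from 0.4 to 0.6: 0.4 × 70% = 28% to 0.6 × 100% = 60%.
- r from 0.5 to 3, p from 0.4 to 0.6: lowest 0.28 / (0.4 + 1.8) = 13%; highest 0.60 / (0.6 + 0.2) = 75%.

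The answer depends almost wholly on inputs that the documents lack.

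**4. What each planned output would show for a group rise in boys that stays within the normal range.**

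- Mean and change tables (SAP 17.3): diluted as in step 1.
- Shift tables and listing flags (SAP 17.3, 17.3.1): nothing, since no value leaves the range.
- Event-of-special-interest tables (SAP 17.1.6, Appendix 2): an entry only if an investigator reports an FSH event. Protocol 6.1.4 makes a laboratory abnormality an adverse event when it is judged clinically significant.

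**The case against.** The strongest reply is that out-of-range values in boys are already covered several times over. All laboratory data are listed with abnormal values flagged (SAP 17.3). The investigator evaluates any change in laboratory values, and a clinically significant abnormality becomes an adverse event (Protocol 6.1.4). FSH increased and decreased are terms of special interest, to be listed and summarised by relationship and severity (SAP 17.1.6, Appendix 2). Medical and safety review runs throughout the study (Protocol 3.2), and the sponsor receives periodic listings (SAP 4.2). The summary tables also give the maximum, which would expose an extreme value.

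This stands. A reader might infer that a male FSH rise would go unseen altogether, or that pooling averages shift counts away as it does means. The documents support neither. What the safeguards do not reach is a group rise inside the normal range.

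A second reply is that no objective or endpoint asks whether FSH rises in males. FSH is called only a potential surrogate, and that sentence in Protocol 6.1.4 is not limited to males. This is also correct: the male concern comes from the risk-benefit section and is not a stated analysis question. It still makes males the group in which a reader will want to see FSH.

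Third, the study is descriptive and has at most 80 subjects. Three age categories split by sex make six cells, and a split could be produced later because sex and FSH are both collected. This limits the weight of the point; it also shows how little the change costs. The output templates named in SAP 8 are not in the text available here, so whether the listings show sex cannot be determined.

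**Conclusion.** The point holds in a limited form. FSH is the only reproductive hormone in the chemistry panel, and the SAP describes no value, change, shift or event summary of it by sex. That absence is clear from SAP 3.3, 7.4 and 17.3. The consequence is confined to group changes in boys within the normal range. If girls do not change on average, the pooled absolute change shows 40% to 60% of the boys' change, given an assumed 40% to 60% boys.

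A reader might go further and say that a 70% to 100% male rise would appear as 35% to 50%. The documents do not support that figure. The rise was seen in Rhesus monkeys at 100 and 300 mg/kg/day, nominally 100/40 = 2.5 to 300/40 = 7.5 times this study's maximum of 40 mg/kg/day. The FSH statement does not give the animals' sex. The figure also needs equal baseline FSH in boys and girls, and the SAP plans absolute change, not percentage change. A loss expressed as mean over standard error would need a ratio of girls' to boys' variability that the documents do not give, in a study that plans no inference.

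This is a cheap and worthwhile improvement to the safety tables. It does not undermine the study's other safety reporting.

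**What to change.** In SAP 17.3, add that FSH will be presented separately for males and females, overall and within age category:

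- actual value and change from each of the two baselines;
- shift against the laboratory's reference range, sex- and age-specific where available.

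In SAP 17.1.6, present the two FSH terms by sex in the same way. Show sex in the FSH listing. State in SAP 7.4 that this display is an exception to the age-only presentation. If the tables have already been produced, add these and label them supplementary.

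The cost is SAP wording and a few descriptive tables. No new data are needed, and there is no error rate to protect because no testing is planned. Cells will be small, so individual FSH values by sex, listed or plotted over time, should accompany the summaries.

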17.3.1. LABORATORY REFERENCE RANGES AND MARKEDLY ABNORMAL CRITERIA

Quantitative laboratory measurements will be compared with the relevant laboratory reference ranges in SI units and categorized as:

- Low: Below the lower limit of the laboratory reference range (LLN).
- Normal: Within the laboratory reference range (upper and lower limit included).
- High: Above the upper limit of the laboratory reference range (ULN).

Document: C:\Users\q832483\Documents\Insy CSR\Pending\Ready for QC\New folder\Statistical Analysis Plan.docx
Author: [REDACTED] Version Number: V1.0 Final
Version Date: 04APR2017

Template No: CS_TP_BS016 – Revision 3
Effective Date: 01May2012

Reference: CS_WI_BS005

STATISTICAL ANALYSIS PLAN: PROTOCOL INS011-14-030

Page 29 of 40

In addition to the high and low quantitative laboratory assignments (as identified by means of the laboratory reference ranges), markedly abnormal values for liver function tests (LFTs) will also be identified and summarized by time point and age category for:

- Alanine aminotransferase (ALT) level >3 times ULN
- Aspartate aminotransferase (AST) level >3 times ULN
- Total bilirubin in excess of >2 times ULN

Markedly abnormal values for LFTs observed at the Follow-up visit will also be summarized by CBD status.

17.3.2. CTC GRADING FOR LABORATORY DATA

Laboratory measurements will not be graded using the Common Toxicity grading (CTC) system.

17.4. ECG EVALUATIONS

Results from the central electrocardiogram (ECG) review will be included in the reporting of this study. If the first ECG is abnormal, up to an additional 2 repetitions of a specific assessment may be performed. ECG will be evaluated at Screening (for subjects who did not meet the rollover timing criteria, see [Section 6.2](#)), Day 1 and at Final Visit/Discontinuation Visit.

The following ECG parameters will be reported for this study:

- HR (Ventricular rate) (bpm)
- PR Interval (msec)
- QRS Interval (msec)
- QT Interval (msec)
- QTcF Interval (msec) [QT interval corrected by Fridericia]
- RR Interval (msec)
- Rhythm
 - Sinus rhythm
 - Atrial fibrillation
 - Other
- Overall assessment of ECG (Investigator's judgment):
 - Normal
 - Abnormal, Not Clinically Significant (ANCS)
 - Abnormal, Clinically Significant (ACS)

Handling of retests values is described [Section 6.3](#).

Document: C:\Users\q832483\Documents\Insy CSR\Pending\Ready for QC\New folder\Statistical Analysis Plan.docx
Author: [REDACTED] Version Number: V1.0 Final
Version Date: 04APR2017

Template No: CS_TP_BS016 – Revision 3
Effective Date: 01May2012

Reference: CS_WI_BS005

The following summaries will be provided for ECG data:

- Frequency counts and shift from baseline by age category (for qualitative measurements) in separate tables
- Summary of absolute results and change from baseline by age category (for quantitative measurements) in separate tables
- Absolute value and change from baseline according to markedly abnormal criteria and age category as described in [Section 17.4.1](#)
- Listing of all data with flag for subjects meeting markedly abnormal criteria for absolute values and for change from baseline

Each ECG result will be compared to the both baselines as defined [Section 6.2](#).

